### **4.5.3. Exploratory Variable(s)**

The exploratory endpoints in the study are

- Change from baseline to week 24 in patient-reported outcome measures in patients with pain due to OA of the knee or hip treated for up to 24 weeks with fasinumab compared to placebo
- Change from baseline to week 24 in patient-reported outcome measures in patients with pain due to OA of the knee or hip treated for up to 24 weeks with fasinumab compared to NSAIDs (pooled celecoxib and diclofenac arms)

- The proportion of patients taking rescue medication, number of days on rescue medication, and weekly average use of rescue medication from baseline to week 24 in patients with pain due to OA of the knee or hip treated for up to 24 weeks with fasinumab compared to placebo
- The proportion of patients taking rescue medication, number of days on rescue medication, and weekly average use of rescue medication from baseline to week 24 in patients with pain due to OA of the knee or hip treated for up to 24 weeks with fasinumab compared to NSAIDs (pooled celecoxib and diclofenac arms)
- Change in WOMAC pain subscale scores from baseline to the average score across Weeks 12, 16, 20 and 24 with fasinumab compared to placebo
- Change in WOMAC physical function subscale from baseline to the average score across Weeks 12, 16, 20 and 24 with fasinumab compared to placebo

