#### Rescue Medications

The number (and percentage) of patients using rescue medication, during the Pre-Treatment Period will be summarized by treatment group and overall based on the SAF. Similar analysis will be performed for the On-Treatment Period based on the SAF.

For patients taking rescue medication, descriptive statistics of the number of days patients took rescue medications will be presented by treatment group during the On-Treatment Period based on the SAF.

For patients taking rescue medication, weekly average usage of rescue medication (measured in mg) is calculated as follows:

$$= \frac{\text{Total amount of rescue medication used in the specified week (in mg)}}{\text{\# of diary entries in the specified week}}$$

Descriptive statistics of the weekly average usage of rescue medications for OA pain will be presented by treatment group based on the SAF.

#### Average WOMAC pain and physical function Score across Week 12 to Week 24

Change in WOMAC pain and physical function subscale scores from baseline to the average score across Weeks 12, 16, 20 and 24 will be analyzed using the same multiple imputation method used to analyze the primary efficacy endpoints in Section 5.7.1. However, the analysis model for the average of the WOMAC subscale scores across multiple visits will instead be an ANCOVA model with terms for baseline WOMAC subscale score, randomization strata (K-L category [2 to 3, or 4], index joint [knee, hip], and geographical region [Europe, North America, Other]) and treatment.

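### Rescue days and weekly rescue amount are summarised only among undefined rescue users, whereas the SAP's own endpoint covers all treated patients, so the user-only means can understate or reverse a difference

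*SAP*

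**What the plan says.** SAP 4.5.3 lists three rescue measures as one exploratory endpoint: "The proportion of patients taking rescue medication, number of days on rescue medication, and weekly average use of rescue medication from baseline to week 24". The population and contrast follow: "in patients with pain due to OA of the knee or hip treated for up to 24 weeks with fasinumab compared to placebo". A second bullet repeats this against the pooled NSAID arms. Neither bullet is limited to patients who used rescue, and nor is the objective in SAP 1.2.3.

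SAP 5.7.5 (Rescue Medications) handles the three measures differently:

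- **Proportion of users.** After a pre-treatment summary in the SAF: "Similar analysis will be performed for the On-Treatment Period based on the SAF". This covers users and non-users.
- **Days.** "For patients taking rescue medication, descriptive statistics of the number of days patients took rescue medications will be presented by treatment group".
- **Weekly amount.** "For patients taking rescue medication, weekly average usage of rescue medication (measured in mg) is calculated as follows". The formula is the week's total mg divided by the number of diary entries in that week. Presentation is then described: "Descriptive statistics of the weekly average usage of rescue medications for OA pain will be presented by treatment group based on the SAF".

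No rule gives a non-user zero. User is not defined as use at any time on treatment or use in the specified week. No between-arm difference is planned for any of the three, although SAP 4.5.3 speaks of comparisons.

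**The concern.** Whether a patient takes rescue on treatment is an outcome that treatment can change. If an effective arm turns light users into non-users, they leave that arm's mean and the heavier users remain. The two user-only means then describe groups selected by response, not the groups as randomised.

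Rescue is available in every arm, and the primary estimand in SAP 5.7.1 is each treatment plus protocol-defined rescue. How much rescue each whole arm consumed is therefore useful context for the WOMAC result. A table headed as rescue use by arm, but computed in users only, could be misread as answering that question.

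**Working it through.** **1. No plan figure to reproduce.** The documents give no expected proportion of users, days or mg. Every rate below is an assumption.

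**2. Identity.** With p the proportion of users and m the mean among users, the all-patient mean is p × m. For fasinumab (F) against a comparator (C):

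- all-patient reduction = 1 − (pF × mF)/(pC × mC)
- user-only reduction = 1 − mF/mC

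The two agree only when pF = pC. Assumed examples for days:

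| Users C / F | Mean days among users C / F | All-patient mean C / F | All-patient reduction | User-only reduction |
|---|---|---|---|---|
| 90% / 90% | 60 / 45 | 54.0 / 40.5 | 25% | 25% |
| 90% / 80% | 60 / 54 | 54.0 / 43.2 | 20% | 10% |
| 80% / 60% | 60 / 54 | 48.0 / 32.4 | 32.5% | 10% |
| 80% / 60% | 60 / 60 | 48.0 / 36.0 | 25% | 0% |
| 80% / 50% | 60 / 66 | 48.0 / 33.0 | 31% | 10% higher |

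The user-only figure can therefore match the all-patient figure, understate it, or point the other way.

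**3. Does the definition of user matter?** Simulated diaries: 168 days (24 × 7), 400,000 patients per setting, beta-distributed daily probability of use (shape 0.3 or 1.0, mean 1, 2 or 4 days per week), with treatment multiplying each patient's probability by 0.7 or 0.5.

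| True all-patient reduction | Among users at any time | Among users in the week |
|---|---|---|
| 30% | 27–30% | 15–27% |
| 50% | 46–50% | 24–45% |

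Users at any time were 76% to more than 99% of the control arm, and users in a given week 41% to 90%. For the 30% case, the any-time definition loses at most about a tenth of the effect ((30 − 27)/30). The by-week definition loses about 10% to 50% ((30 − 27)/30 to (30 − 15)/30).

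**4. Does the proportion of users matter?** Threshold model: use = max(0, N(μ, 1)), with all-patient mean μΦ(μ) + φ(μ) and proportion of users Φ(μ). For μ = 0.5 against 0.1, users are 69% against 54%. All-patient means are 0.698 and 0.451 (35% lower); user means are 1.009 and 0.835 (17% lower). With the same 0.4 SD shift and more control users:

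| Control users | All-patient reduction | User-only reduction |
|---|---|---|
| 69% | 35% | 17% |
| 80% | 31% | 18% |
| 90% | 26% | 18% |
| 95% | 22% | 17% |

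The gap narrows from 18 to 5 percentage points as nearly everyone becomes a user.

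**5. What can be recovered from the planned tables?**

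- *Days:* the proportion of users and the mean among users are both planned for the on-treatment period in the SAF. Their product is the all-SAF mean, with every patient without recorded use counted as zero. The all-patient median and quartiles do not follow from it.
- *Weekly amount, any-time users:* the same multiplication applies in principle.
- *Weekly amount, users in the week:* a weekly proportion of users is needed and is not planned. The SAP's standard summaries give n, but not the number of patients with diary entries that week, so the denominator is missing.

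**6. The ratio.** With seven entries and 3,000 mg in the week, the formula gives 3,000/7 ≈ 429 mg. That is a mean daily amount within the week.

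**The case against.** The strongest reply has four parts.

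- **The proportion of users is reported for the full SAF.** A proportion plus an amount among users is a recognised two-part summary, and for days it yields the all-patient mean exactly. This stands for days. It does not stand for weekly amount under a by-week definition.
- **Most patients may use rescue at some point.** They were regular NSAID users, had WOMAC pain of at least 4, discontinued other pain medication, and may take acetaminophen for OA pain, other pain or fever over 24 weeks. A high any-time rate is plausible, and masking would then be small. This is inference, since the documents give no rate, and it does not help if users are counted week by week.
- **Presentation is stated to be based on the SAF.** That wording leaves some ambiguity, but the formula is introduced only for users and no zero rule follows, so it does not settle the matter.
- **The division by diary entries is deliberate.** SAP 5.7.5 averages the walking-pain NRS over non-missing days in the same way, and the choice changes no relative comparison between arms. This stands; only the label needs attention.

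A reader might infer that the user-only summaries hide most of any reduction, or always push towards no difference. The documents do not support either: equal proportions of users give no masking, and other inputs give a reversal. Nor is it right that the proportion of users can never repair the mean, because for days it does.

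**Conclusion.** The mismatch between SAP 4.5.3 and SAP 5.7.5 is real and rests on stated wording: the endpoint covers treated patients, while two of its three summaries cover users only, with user undefined and non-users given no zero. User-only means are not comparisons of the randomised groups and can understate or reverse a difference in use.

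Size and direction cannot be determined from the documents. Under the assumed models, masking is small when nearly all patients use rescue at some time. It is larger when users are defined by week, or when treatment acts mainly on whether rescue is used. The lasting information loss is confined to the all-patient weekly amount under a by-week definition.

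The endpoint is exploratory, descriptive and outside the H1–H6 testing order, so type I error and power are unaffected. Priority is minor.

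**What to change.** In SAP 5.7.5:

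1. Summarise days on rescue and rescue amount by arm in all SAF patients with diary data, entering zero where the diary confirms no use. State how many patients contribute in each week.
2. Add descriptive fasinumab–placebo and fasinumab–pooled-NSAID differences, to match SAP 4.5.3.
3. Define user as use at any time on treatment or use in the specified week, and keep the user-only figures as a supplement under that definition.
4. Label the ratio as mean daily mg within the week.

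Protocol 7.2 already has rescue use reported daily by diary during treatment, so zero use is observable. The cost is a few lines of SAP text and a changed denominator in the tables; no new data are needed.

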#### **5.7.6. Analysis of Quality-of-Life and Health Economic Variables**

The following patient reported outcomes will be summarized and analyzed. Analysis results for exploratory objectives will be included in the final CSR.

#### EuroQol 5 Dimensions 5 Level Questionnaire (EQ-5D-5L)

The health states defined by the 5-dimensional classification will be converted into the corresponding index score. The EQ-5D-5L index will be set to missing if any of the 5 dimensions is missing.

An MMRM model will be fit to the EQ-5D-5L Visual Analog Scale and index scores include the randomization strata (K-L category [2-3 vs. 4], index joint [hip or knee] and geographic region), treatment, visit, treatment-by-visit interaction as fixed effects, and baseline value as a covariate. The least-squares (LS) means for the mean change from baseline to each visit, as well as the LS mean differences between fasinumab and placebo and NSAID groups, with their corresponding standard errors (SEs), p-values and associated 95% confidence intervals, will be provided from the MMRM.

#### 36-Item Short Form Medical Outcome Study Questionnaire, Version 2 (SF-36)

The same analysis used for the EQ-5D-5L will be performed for the subscale scores of the SF-36 using analogous MMRM models. SF-36 subscale scores will be computed if at least 50% of component items are available. The missing items will be imputed by the mean of available items.

#### Health Care Resource Utilization Questionnaire (HCRU)

The utilization of each resource captured on the HCRU will be summarized via descriptive statistics by treatment group for each visit.

#### Work Productivity and Activity Impairment-Osteoarthritis (WPAI-OA)

The number and percentage of patients who reported they were working/non-working on Question 1 of the WPAI-OA will be presented by treatment group for each visit. Furthermore, for patients who answered 'YES' to Question 1 at that visit, the absenteeism, presenteeism, work productivity loss and activity impairment scores will also be constructed. The same analysis used for the EQ-5D-5L will be presented for all four scores of the WPAI-OA using analogous MMRM models.

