### **8.2.2.4. Work Productivity and Activity Impairment**

The work productivity and activity impairment-osteoarthritis questionnaire is a validated measure of impairments in work and daily activities ([Reilly 1993](#)) ([Zhang 2010](#)). Patients will complete the questionnaire at time points indicated in [Table 1](#).

A copy of the assessment is provided in the study reference manual.

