#### **4.10. Health Economic Variables**

The following patient reported health economic outcome measures will be summarized:

- HealthCare Resource Utilization (HCRU) including total and type of usage and hospitalizations
- Change from baseline by visit in the WPAI-OA item and sub scores including absenteeism, presenteeism, work productivity loss and activity impairment

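### WPAI-OA activity impairment is scored only for patients working at each visit, which discards non-workers' daily-activity data and selects on a post-randomisation status

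*SAP*

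**What the plan says.** **SAP 5.7.6, WPAI-OA.** Counts and percentages for "patients who reported they were working/non-working on Question 1 of the WPAI-OA will be presented by treatment group for each visit", so Question 1 is the employment question and is read again at every visit. One clause, covering those whose answer is YES, then sets the scope: "to Question 1 at that visit, the absenteeism, presenteeism, work productivity loss and activity impairment scores will also be constructed". All four scores are named under that condition, activity impairment among them. The analysis follows: "The same analysis used for the EQ-5D-5L will be presented for all four scores of the WPAI-OA using analogous MMRM models".

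**SAP 5.7.6, EQ-5D-5L.** The model being borrowed contains the randomisation strata, "treatment, visit, treatment-by-visit interaction as fixed effects, and baseline value as a covariate".

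**SAP 4.10.** The variable is change from baseline by visit in the WPAI-OA item and "sub scores including absenteeism, presenteeism, work productivity loss and activity impairment". No employment condition is attached.

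**Protocol 8.2.2.4.** The instrument is described as "a validated measure of impairments in work and daily activities". Patients complete it at the Table 1 time points (baseline and weeks 4, 8, 12, 16, 20 and 24), with no exemption for those not in work.

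Neither document specifies an activity-impairment analysis for non-workers. SAP 5.7.6 gives no reason for the restriction, and SAP 1.2.4 does not list it.

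**The concern.** Absenteeism, presenteeism and work productivity loss have no meaning for someone without a job, so limiting them to workers is reasonable. Activity impairment is different: a retired patient with knee or hip OA has daily activities that the disease can impair. Putting this score under the same condition causes two separate problems.

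1. **Loss of data.** Answers from non-workers are left out. Inclusion criterion 1 sets a minimum age of 18 with no upper limit, no listed criterion requires employment, and SAP 4.1 plans age groups of 65-74 and 75 or over. The excluded part may well be large.
2. **Selection after randomisation.** Inclusion at each visit depends on work status at that visit. If treatment changes pain or function it may also change who is working, so the treated and control patients compared at a given visit need not be alike. A restriction on baseline employment alone would lose data but would not have this second problem.

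At stake is one modelled patient-reported comparison against placebo and against NSAIDs. It would be less precise than it need be, and it would lose the protection that randomisation gives.

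**Working it through.** The plan states no figure for this endpoint, so there is none to reproduce. The check is a reading of the rule, followed by illustrations of its cost.

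**Step 1: follow the rule literally.**
- Not working at baseline: no baseline score. The model needs the baseline value as a covariate, so the patient contributes nothing at any visit, even if working later.
- Working at baseline but not at week *t*: no score at week *t*. The MMRM handles that visit as missing at random, which the SAP does not justify.
- A visit therefore counts only if the patient works both at baseline and at that visit.

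**Step 2: loss of precision.** Inputs are 1500 randomised patients (600 fasinumab, 600 pooled NSAIDs, 300 placebo; SAP 2.2), the 20% dropout assumed there, and a working share *w*, which is an **assumption** because the documents do not give it.

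Eligible patients = 1500 × *w*. Standard-error factor = 1/√*w*, assuming equal residual variance in workers and in all respondents, and the same share in each arm.

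As a yardstick for power I use an effect size of 0.22, borrowed from the WOMAC pain comparison with NSAIDs in SAP 2.2; the plan assumes nothing for WPAI-OA. Power ≈ Φ(0.22 × √[n₁n₂/(n₁+n₂)] − 1.96). With all patients against NSAIDs, n₁ = n₂ = 480, giving Φ(0.22 × √240 − 1.96) = Φ(1.448) = 0.926, in line with the 92% the plan states for that effect size. With *w* = 0.5, n₁ = n₂ = 240, giving Φ(0.22 × √120 − 1.96) = Φ(0.450) = 0.674.

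| Assumed *w* | Eligible | Excluded | SE factor | Power vs NSAIDs | Power vs placebo |
|---|---|---|---|---|---|
| 100% | 1500 | 0 | 1.00 | 0.926 | 0.795 |
| 80% | 1200 | 300 | 1.12 | 0.862 | 0.702 |
| 50% | 750 | 750 | 1.41 | 0.674 | 0.503 |
| 30% | 450 | 1050 | 1.83 | 0.463 | 0.332 |
| 20% | 300 | 1200 | 2.24 | 0.332 | 0.237 |

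**Step 3: effect of selection.** A simulation took a true treatment difference of −0.30 SD in impairment and let the log-odds of working fall with impairment. The slopes and the control-arm working shares (30% and 50%) are assumptions.

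| Fall in log-odds of working per SD of impairment | Difference among workers | Working share, treated (control 30%) | Working share, treated (control 50%) |
|---|---|---|---|
| 0 | −0.300 | 30.0% | 50.0% |
| 0.5 | −0.284 | 33.1% | 53.5% |
| 1.0 | −0.249 | 35.6% | 56.2% |

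If working does not depend on impairment there is no bias. If it does, the difference among workers shrinks toward zero in these scenarios, because treatment keeps some more impaired patients in work.

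**The case against.** The strongest points on the other side are these.

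- **It may be a drafting slip.** SAP 4.10 defines the variable without an employment condition, and the sentence in 5.7.6 may simply have compressed four scores into one list. That is possible, but 4.10 supplies no method for non-workers, and 5.7.6 is the only text a programmer has. Protocol 10.5 defers to instrument manuals for missing items, not for who receives a score.
- **The items are not shown.** The questionnaire is in the study reference manual, so the documents do not prove that a patient answering NO to Question 1 goes on to the activity item. This stands as a caveat. The protocol's description of the instrument makes it likely, and the proposed wording covers either case.
- **Selection on work status affects the three work scores too.** True. For those scores the condition cannot be avoided; for activity impairment it can.
- **The size is unknown, and selection may be slight.** Both are fair. Age groups do not give employment rates, nothing in the documents shows that treatment changes employment within 24 weeks, and the simulated bias is modest.
- **Little depends on it.** This also stands. WPAI-OA is a health-economic variable outside H1 to H6. Function is also measured without an employment condition by WOMAC physical function, SF-36 and EQ-5D-5L.

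These points limit the importance of the concern. None gives a reason to keep the condition on a daily-activity score.

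**Conclusion.** The concern holds. Followed as written, SAP 5.7.6 gives non-workers no activity-impairment score, removes anyone not working at baseline from the model, and makes each later comparison depend on a status that can change after randomisation. At an assumed working share of 30% to 50%, the standard error is 1.83 to 1.41 times that from all respondents. Even at 80% working, 300 of 1500 randomised patients would be excluded. These figures rest on the assumed share, on equal variance, and on non-workers answering the activity item. Any bias from selection cannot be sized from the documents. The primary and key secondary analyses are untouched, so this is a low-priority correction, but a clear one.

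**What to change.** In SAP 5.7.6, take activity impairment out of the Question 1 condition. Construct it for every patient who answers the activity item, whatever the answer to Question 1, and fit the planned MMRM to all of those patients. Keep the YES condition for absenteeism, presenteeism and work productivity loss, and state that those three results describe patients in work at the visit rather than all randomised patients.

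The cost is one amended sentence plus that short note. The questionnaire is already scheduled, so no new visit or assessment is needed, and the testing hierarchy does not change.

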### Treatment Satisfaction Questionnaire for Medicine (TSQM)

The same analysis used for the EQ-5D-5L will be performed for the effectiveness, side effects, convenience and global satisfaction domain scores of the TSQM using analogous MMRM models. The missing items will be imputed by the mean of available items.

## **5.8. Analysis of Safety Data**

The analysis of safety and tolerance will be performed on the SAF, as defined in Section 3.4.

The safety analysis will be based on the reported AEs and other safety information (clinical laboratory evaluations, vital signs and 12-lead ECG).

Thresholds for Potential Clinically Significant Values (PCSV) in laboratory variables, vital signs and ECG are defined in Section 10.3.

The summary of safety results will be presented for each treatment group and by visit where applicable.

Day 1 is the first day of investigational product, Day –1 is the day before; there is no Day 0.

The time interval to detect any AEs, including AESIs (except JR identified at the 72-week telephone follow-up), or abnormalities is between the first dose of study drug dose up to the end of the Follow-Up Period (i.e., week 44/Early Termination). Any study drug-related SAEs occurring between the end of Follow-Up clinic visit and the End of Study will also be included. Data collected outside this interval will be excluded from the descriptive statistics and identification of abnormalities for laboratory evaluations, ECGs and vital signs. All post-baseline data during the interval will be used in the PCSV analysis including scheduled and unscheduled assessments.

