#### **8.2.3.10. Procedures to be Performed Only in the Event of a Joint Replacement Surgery**

In the event that a patient must undergo JR surgery during the treatment or follow-up periods, the patient will be discontinued from study drug and asked to return for a pre-operative visit. The pre-operative visit should be completed before JR surgery if possible and pre-operative images will be submitted to the adjudication committee for review. Following the JR surgery, the patient will complete follow-up safety evaluations at 4 weeks and 20 weeks after surgery (see [Table 2](#)).

In the event that the pre-operative visit is not performed, standard-of-care pre-operative images of the joint with JR must be obtained and submitted to the central imaging vendor's adjudication committee for review. Imaging of all other joints per the pre-operative visit procedures will be done post-operatively at the first JR follow-up study visit (4 weeks after surgery) if not done before surgery.

All available medical history/information for patients who undergo JR surgery must be collected, including placement of prosthesis, healing of the surgical wound and the results of histopathologic examination.

Full details of these assessments are provided in the study reference manual.

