### 9.4.2. Serious Adverse Events

All SAEs, regardless of assessment of causal relationship to study drug, must be reported to the sponsor (or designee) within 24 hours. Refer to the study reference manual for the procedure to be followed.

Information not available at the time of the initial report must be documented in a follow-up report. Substantiating data such as relevant hospital or medical records and diagnostic test reports may also be requested.

In the event the investigator is informed of an SAE after the patient completes the follow-up period (week 44)/early termination visit, the following will apply:

- SAE with an onset within 30 days of the end of the follow-up period (week 44)/early termination visit - the SAE will be reported to the sponsor. The investigator should make every effort to obtain follow-up information on the outcome until the event is considered chronic and/or stable.
- SAE with an onset day greater than 30 days from the end of the follow-up period (week 44)/early termination visit - only SAEs deemed by the investigator to be drug-related will be reported to the sponsor. The investigator should make every effort to obtain follow-up information on the outcome of a drug-related SAE until the event is considered chronic and/or stable.
- SAE reported by the patient at the end of study phone call and deemed by the investigator to be drug-related will be reported to the sponsor. The investigator should make every effort to obtain follow-up information on the outcome of a drug-related SAE until the event is considered chronic and/or stable.

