#### 10.4.4. Safety Analysis

Safety data including TEAEs and treatment emergent AESIs, vital signs, physical examinations, laboratory tests, ECGs, and ADA formation will be listed and summarized by treatment group.

Thresholds for potentially clinically significant values in laboratory parameters and vital signs will be defined by the sponsor and be in effect at the time of final SAP approval.

The time interval to collect any AEs, including AESIs, is between the first dose of double-blinded study drug injection and the week 44 visit, as well as study drug-related SAEs occurring between the week 44 visit and the end of study.

For safety variables, 3 observation periods are defined:

- The pretreatment period is defined as the time from signing the ICF to before the first dose of study drug
- The treatment period is defined as the day of the first dose of study drug through to the day of the last dose of study drug (week 20) + 4 weeks.
- The follow-up period is defined as from the end of the on-treatment period (week 24) to the week 44 visit.

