## 5. STATISTICAL METHODS

For continuous variables, descriptive statistics will include the following: the number of patients reflected in the calculation (n), mean, median, standard deviation, minimum & maximum and 1st & 3rd quartiles (Q1 & Q3).

For categorical or ordinal data, frequencies and percentages will be displayed for each category.

**Period of Observation** - Unless otherwise stated, analysis of all safety and non-safety variables captured at multiple visits will be analyzed by the following observation periods:

- The Pre-Treatment Period is defined as the time from signing the ICF to before the first dose of study drug.
- The On-Treatment Period is defined as the time from the first dose of study drug up to 28 days after the last dose of study drug.
- The Follow-Up/Post-Treatment Period is defined from the end of the On-Treatment Period to the date of the follow-up clinic visit (Week 44 visit) or early termination date.

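### The safety interval stops at Week 44 or early termination and then admits only drug-related SAEs, which does not match the 30-day all-cause SAE reporting rule or, for some early withdrawers, the SAP's own On-Treatment Period

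*SAP*

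**What the plan says.** SAP 5.8 sets the interval: "The time interval to detect any AEs, including AESIs (except JR identified at the 72-week telephone follow-up), or abnormalities is between the first dose", and it runs "up to the end of the Follow-Up Period (i.e., week 44/Early Termination"). It then adds one class of later event: "Any study drug-related SAEs occurring between the end of Follow-Up clinic visit and the End of Study will also be included". The next sentence removes out-of-interval data, but in these terms: "Data collected outside this interval will be excluded from the descriptive statistics and identification of abnormalities for laboratory evaluations, ECGs and vital signs".

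Protocol 10.4.4 has the same rule. To the AEs up to Week 44 it adds later ones in the words "as well as study drug-related SAEs occurring between the week 44 visit and the end of study". It refers only to the Week 44 visit, not to ET, and has no exception for JR.

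Protocol 9.4.2 treats later SAEs in two steps. An "SAE with an onset within 30 days of the end of the follow-up period (week 44)/early termination visit" goes to the sponsor with no condition on causality. Only SAEs with later onset are limited to those the investigator judges drug-related. Both steps apply when the investigator is informed of the event.

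SAP section 5 defines the observation periods: "The On-Treatment Period is defined as the time from the first dose of study drug up to 28 days after the last dose". The Post-Treatment Period runs from there to the Week 44 visit or the ET date.

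For JR, protocol 8.2.3.10 says that "the patient will complete follow-up safety evaluations at 4 weeks and 20 weeks after surgery". Protocol Table 2 has an adverse-event row and bilateral X-rays for those visits. SAP 5.8.7 analyses time to JR in any study period and censors time to adjudicated arthropathy (AA) and destructive arthropathy (DA) at the last visit.

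**The concern.** Protocol 9.4.2 says which late SAEs reach the sponsor, and SAP 5.8 says which of them are analysed. The two differ for 30 days. In that time an SAE counts under the stated interval only if one investigator has called it drug-related, although the protocol asks for it regardless.

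The mismatch is sharper for a patient who leaves the study soon after a dose. SAP section 5 calls an event on-treatment up to 28 days after the last dose, and protocol 10.4.4.1 defines treatment-emergent AEs by the on-treatment period. SAP 5.8 may already have closed the interval at the ET visit. Two programmers following different sections would count the same serious event differently.

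A smaller ambiguity of the same kind affects AA and DA found at visits after JR. Incidence of AA and of DA are named safety endpoints (protocol 4.3), and two higher-dose regimens were stopped in this programme after imbalances that included time to joint replacement. The rule for what counts late in the study should be unambiguous.

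**Working it through.** The documents give no figure for this point, so there is none to reproduce. The check is study-day arithmetic, then a rough size.

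1. **Calendar.** Study day = 7 × week + 1. Week 44 is Day 309 and Week 72 is Day 505 (= Day 141 + 364), as scheduled. The 30 days after a Day 309 visit are Days 310 to 339, out of 505 − 309 = 196 days to the final call. An unrelated SAE in Days 310–339 is reportable under 9.4.2 and outside the 5.8 interval. The post-treatment SAE table does not settle it, because the Post-Treatment Period also ends at Week 44/ET. The on-study SAE and deaths outputs in SAP 5.8.1 have no stated time limit.

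2. **Early withdrawal.** Let the last dose of any study drug be on day L and the ET visit on day E. The On-Treatment Period ends on L + 28 and the 5.8 interval on E. If E − L < 28, the interval closes 28 − (E − L) days too early. Example: L = 57, E = 62, SAE judged unrelated on Day 75.
   - On-treatment to 57 + 28 = Day 85, so Day 75 is on-treatment.
   - Reportable under 9.4.2 to 62 + 30 = Day 92, so Day 75 is reportable.
   - The 5.8 interval closed on Day 62, so Day 75 is outside it. The gap is 28 − 5 = 23 days.
   - The Post-Treatment Period would start after Day 85 and end on Day 62, so section 5 does not work for this patient either.

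   The protocol asks for the ET visit as soon as possible (Table 1, footnote 1), so E − L < 28 can readily occur.

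3. **Size.** Input from the documents: 1500 patients. Assumed, because the documents give no value: an all-cause SAE rate of 4–8 per 100 patient-years, 80–95% judged unrelated, and every late SAE reported.
   - 1500 × 30 / 365.25 = 123 patient-years
   - 123 × 0.04 to 0.08 = 4.9 to 9.9 SAEs
   - Low: 4.9 × 0.80 = 3.9. High: 9.9 × 0.95 = 9.4. That is about 4 to 9 SAEs over all arms.

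4. **Visits after JR.** Table 2 places the later visit on follow-up Day 140. With JR on day D, it passes Day 309 when D + 140 > 309, that is D > 169 (170 if surgery is follow-up Day 1). The 4-week visit passes Day 309 only when D is later than about Day 280–281, near Week 40. A JR at Week 16 has visits at Weeks 20 and 36, both inside. A JR at Week 28 has them at Weeks 32 and 48, and one at Week 44 at Weeks 48 and 64. So for patients on the regular schedule only JRs after about Day 169 are affected. An AA first seen at such a visit could enter the time-to-event display of 5.8.7, if that visit is the last visit, yet fall outside the interval for the AESI incidence tables of 5.8.2.

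**The case against.** The strongest reply is that little is actually excluded. The only explicit exclusion in 5.8 names laboratory, ECG and vital-sign data. The on-study AE and SAE tables, the deaths output and the listings of deaths and JRs carry no causality limit, and the 120-day safety update in SAP section 7 takes additional safety data to its cut-off. On this view the Day 75 event is simply a serious TEAE. This stands against any claim that such events are certainly lost, or that deaths are under-counted: a reader might infer either, but the documents do not show it. It does not supply a rule, because on study is undefined and 5.8 states an interval that leaves these SAEs out.

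A reader might also infer that joint events found after JR are dropped. The documents do not support that. JR found at the 72-week call is excepted in 5.8, JR is analysed in any period, and the AA/DA time-to-event analyses have no Week 44 cut-off. What remains is the AESI incidence tables and the meaning of last visit.

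Three further points are fair. The SAP is not departing from the protocol's statistical section, since 10.4.4 has the drug-related-only rule; the protocol is itself inconsistent between 9.4.2 and 10.4.4. A reporting duty and an analysis window need not coincide, and closing at the last scheduled clinic visit, where ascertainment is uniform, is defensible. Reporting after Week 44 is passive, with no scheduled contact in the 30 days. These limit the size of the problem. They do not explain an interval that can close inside the On-Treatment Period.

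**Conclusion.** The concern holds as a mismatch of definitions with a small likely effect. Unrelated SAEs with onset in the 30 days after Week 44/ET are reportable but outside the stated analysis interval, and no output is defined clearly enough to settle their place. For patients whose ET visit comes less than 28 days after the last dose, SAP section 5 and SAP 5.8 disagree on whether a serious on-treatment event counts.

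The 4 to 9 SAEs are an upper range. They rest on assumed event and causality rates, a full 30 days for all 1500 patients, and complete reporting under a passive rule. A reader might go on to infer unequal loss between arms, but nothing in the documents shows it. No efficacy result is touched. The JR part is a request for definition, limited on the regular schedule to JRs after about Day 169.

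**What to change.** 1. In SAP 5.8 and protocol 10.4.4, include all SAEs and deaths regardless of causality with onset up to 30 days after Week 44/ET, and never end the interval before last dose plus 28 days. After that, keep drug-related SAEs as now. If the protocol is not amended again, record the change in SAP 1.2.4.
2. Define on study in SAP 5.8.1 to match, and note that ascertainment after Week 44 is passive.
3. State that AA and DA found at Table 2 visits count in the AESI incidence tables, that last visit in the 5.8.7 censoring rule includes those visits, and whether the combined ET/JR pre-operative visit closes the interval.
4. Reconcile protocol 9.4.1, which stops AE recording at Week 44, with 9.4.6 and Table 2, which continue it.

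The cost is wording and a derivation change. The late SAEs already go to the sponsor under 9.4.2, so no new collection is needed, but the team should confirm that they reach the analysis data despite 9.4.1. SAE counts may rise slightly. Patients with JR are observed longer, which the time-to-event displays handle.
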